5.0 TREATMENT PLAN

5.1 Treatment Dosage and Administration

Protocol treatment must start within 14 business days of enrollment to the study.

- 5.1.1 In this study, Cohort A and Cohort B patients will start treatment with nivolumab dosed at 3 mg/kg IV and ipilimumab 1 mg/kg every 3 weeks for up to 4 doses. Cohort C patients will receive immunotherapy with nivolumab dosed at a flat dose of 480 mg IV every 4 weeks for up to 26 doses or 104 weeks.
- 5.1.2. Cohorts A and B maintenance immunotherapy with nivolumab dosed at a flat dose of 480 mg IV every 4 weeks will be continued for up to 23 doses or 92 weeks. Missed doses of 480 mg Nivolumab due to toxicity or general health condition will be skipped.

5.1.3 Total protocol therapy for all Cohorts will be up to 104 weeks during treatment. If disease progression or recurrence occurs during the follow-up phase, then per treating physician discretion, the patient may resume nivolumab 480 mg IV every 4 weeks until progression if tolerated with axial imaging as per protocol every, 12 weeks.

5.1.4 All study therapy will be administered on an outpatient basis.

Agent	Precautions	Dose	Route	Schedule	Cycle Length
Nivolumab (solution for injection) induction Cohort A and B only	Administer before other immunotherapy agents	3 mg/kg up to 4 doses	IV infusion over 30 minutes, +/- 10 minutes, with a sterile, nonpyrogenic, low protein binding 0.2 to 1.2 micrometer in-line filter. Follow with saline flush.	Day 1	3 weeks
Ipilimumab (solution for injection) induction Cohort A and B only	Administer 30 minutes after nivolumab.	1 mg/kg up to 4 doses	IV infusion over 90 minutes, +/- 10 minutes, through a non-pyrogenic, low protein-binding in-line filter. Separate IV line required.	Day 1	3 weeks
Nivolumab (solution for injection) maintenance After induction in Cohorts A and B; and throughout in Cohort C	Administer before other immunotherapy agents	480 mg up to 23 doses (92 weeks in Cohort A and B, and 104 weeks in Cohort C)	IV infusion over 30 minutes, +/- 10 minutes, with a sterile, nonpyrogenic, low protein binding 0.2 to 1.2 micrometer in-line filter. Follow with saline flush.	Day 1	4 weeks

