5.2 Toxities and Dosing Delays/Dose Modifications

Any patient who receives treatment on this protocol will be evaluable for toxicity. Each patient will be assessed for the development of toxicity according to the Time and Events Table (Section 6.1). Toxicity will be assessed according to the NCI Common Terminology Criteria for Adverse Events (CTCAE), version 4.03. Dose changes of either study drug is NOT permitted. Doses can be held however as necessary. Dosing holds should be made according to the system showing the greatest degree of toxicity.

Adverse Event Related vs Unrelated Dose Delays: If dose delay is due to an unrelated Adverse Event then reason for hold must be documented. Any patient on this protocol will be allowed to continue to receive study treatment at the investigator's discretion, regardless of AE relatedness. Do not have to delay dose for unrelated Adverse Event.

5.2.1 Treatment delay for toxicity of more than 84 days from last intended therapy will result in treatment discontinuation for the specific drug(s) responsible for the toxicity. If ipilimumab is permanently discontinued, then discontinue Nivolumab 3mg/kg. Nivolumab 480 mg can be continued.

5.2.2 Investigators should consider dose re-calculation of ipilimumab with change in weight as per standard of care/institutional guidelines. However, a change in weight by 10% or more should lead to a dose re-calculation.

5.2.3 Nivolumab and/or ipilimumab cannot be dose reduced in response to toxicity, and can only be held or discontinued as per detailed algorithms for immune-therapy toxicity management below.

NCI CTCAE v 4 Grade	Nivolumab	Ipilimumab
0-1	No change from original starting dose	No change from original starting dose
2	Withhold drug, resume treatment when adverse reaction improves to grade 0 or 1	Withhold drug, resume treatment when adverse reaction improves to grade 0 or 1
3	Withhold drug, resume treatment when adverse reaction improves to grade 0 or 1 when given as a single agent	Withhold drug, resume treatment when adverse reaction improves to grade 0 or 1
Second episode of grade 3 or any episode of grade 4 toxicity	Permanently discontinue therapy and remove subject from trial	Permanently discontinue therapy and remove subject from trial

Certain adverse events that are possibly immune mediated warrant special monitoring and management, and are outlined below to guide investigators.

5.2.4.1 Pulmonary:

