Rule out non-inflammatory causes. If non-inflammatory cause, treat accordingly and continue protocol therapy. Evaluate with imaging and pulmonary consultation.

Grade of pneumonitis (NCI CTCAE v4)	Management	Follow-up
Grade 1 Radiographic changes only	
Consider delay nivolumab or ipilimumabMonitor for symptoms every 2-3 daysConsider pulmonary and infectious disease consultations	
Re-image at least every 3 weeks 
If worsens:
 
If worsens:
 
Treat as Grade 2 or 3-4

Grade 2 Mild to moderate new symptoms	
 Delay nivolumab or ipilimumab Consult pulmonary and infectious disease Monitor symptoms daily, consider hospitalization 1.0-2.0 mg/kg/day methylprednisolone IV or oral equivalent Consider bronchoscopy and/or lung biopsy 	
 Re-image every 1-3 days 
If improves: If improves:
 
 When symptoms return to near baseline, taper steroids over at least one month and resume nivolumab and ipilimumab per protocol and consider prophylactic antibiotics 
If not improving after 2 weeks or worsening:
 
 Treat as Grade 3-4 
If not improving after 2 weeks or worsening, treat as grade 3 or 4

Grade 3 or 4 Severe new symptoms; New/worsening hypoxia; Life-threatening	
 Discontinue nivolumab or ipilimumab Hospitalize Consult pulmonary and infectious disease 2-4 mg/kg/day methylprednisolone IV or IV equivalent Add prophylactic antibiotics for opportunistic infections Consider bronchoscopy and/or lung biopsy 	
If improves to baseline:
 
 Taper steroids over 6 weeks 
If not improving after 48 hours or worsening:
 
 Add additional immunosuppression

5.2.4.2 Gastrointestinal:

Rule out non-inflammatory causes. If non-inflammatory is identified, treat accordingly and continue protocol therapy. Opiates/narcotics may mask symptoms of perforation. Infliximab should not be used in case of perforation or sepsis.

Grade of diarrhea/colitis (NCI CTCAE v4)	Management	Follow-up

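### After a first grade 3 toxicity, section 5.2.3 allows a restart where five organ tables in 5.2.4 stop treatment, with no stated precedence, and its grade 3 row is unusable during combination dosing

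*Combined protocol and SAP*

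**What the plan says.** Section 5.2.3 forbids dose reduction and gives a general table by CTCAE grade. For grade 3, the nivolumab cell is "Withhold drug, resume treatment when adverse reaction improves to grade 0 or 1 when given as a single agent". The ipilimumab cell has the same hold-and-restart rule without the last condition. The row below covers a second grade 3 or any grade 4 event and says "Permanently discontinue therapy and remove subject from trial", so the grade 3 row is about the first episode.

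Section 5.2.4 then gives organ-specific management. The grade 3–4 rows for pulmonary, gastrointestinal, hepatic and neurological events say "Discontinue nivolumab or ipilimumab" (the gastrointestinal row adds that this is per protocol), and none has a restart step. The myocarditis table makes the grade 3 stop permanent. The renal and skin tables allow treatment to resume.

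Three further passages bear on how to read these rules:

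- Section 5.2.3 introduces the rules by saying the drugs "can only be held or discontinued as per detailed algorithms for immune-therapy toxicity management below", and the sentence after the table says the organ-specific measures "are outlined below to guide investigators".
- The agent table in 5.1 says of ipilimumab "Administer 30 minutes after nivolumab". No regimen in 5.1 gives ipilimumab alone.
- Section 5.2.1 says: "If ipilimumab is permanently discontinued, then discontinue Nivolumab 3mg/kg. Nivolumab 480 mg can be continued".

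**The concern.** A first grade 3 immune-mediated event is foreseeable in this trial, and the protocol gives two instructions for it. A site that follows the general table restarts drug after, say, a grade 3 pneumonitis that has settled to grade 1. A site that follows the organ table stops. Both can say they followed the protocol. In a multicenter trial this is primarily a safety matter.

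It also reaches the results. Section 11.3 reports the proportion of patients removed from treatment for adverse events, overall and by cohort, and describes duration of therapy. Both would partly reflect which table a site chose.

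During combination dosing there is a second problem inside the general table itself: the two grade 3 cells do not give a workable restart instruction.

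**Working it through.** No arithmetic settles this, so the rules are set side by side for a first grade 3 event. The general rule in 5.2.3 is to withhold and resume at grade 0 or 1. I read *nivolumab or ipilimumab* in the organ rows as whichever study drug the patient is receiving.

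| Organ table | Grade 3 instruction | Restart step at grade 3 | Grade 2 row, for comparison | Against 5.2.3 |
|---|---|---|---|---|
| 5.2.4.1 Pulmonary | Discontinue | None | Delay, then resume | Conflict, by inference |
| 5.2.4.2 Gastrointestinal | Discontinue, per protocol | None | Delay, then resume | Conflict, by inference |
| 5.2.4.4 Hepatic | Discontinue | None | Delay, then resume | Conflict, by inference |
| 5.2.4.5 Neurological | Discontinue | None | Delay, then resume | Conflict, by inference |
| 5.2.4.8 Myocarditis | Permanently discontinue | None | Delay, retreatment possible | Conflict, explicit |
| 5.2.4.6 Skin | Delay or discontinue | At grade 1 | Continue, delay if persistent | None |
| 5.2.4.7 Renal | Delay (grades 2–3 share a row) | At grade 1 | Same row | None |

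Count: 1 explicit + 4 by inference = 5 of 7 graded tables in conflict; 2 of 7 not. Endocrinopathy is not graded and is left out.

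The inference for the four tables rests on their own contrast. At grade 2 each says delay and names a restart; at grade 3 each changes the verb and drops the restart.

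**Precedence.** Calling the rules detailed algorithms, and describing certain events as needing special management, favors the organ rows. Describing those rows as guidance weakens that, as does the gastrointestinal row's reference back to the protocol. The 5.2 sentence about the system with the greatest toxicity ranks organ systems, not the two sets of tables. The discretion sentence says patients are "allowed to continue to receive study treatment" but not which drug or under which table.

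**The grade 3 row during combination dosing.** There are two readings of the nivolumab condition.

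1. Nivolumab may restart only as a single agent. Restarting both drugs breaks the nivolumab cell. Restarting ipilimumab alone departs from 5.1. Moving to nivolumab 480 mg leaves the ipilimumab permission unused. The cells contradict each other.
2. The cell applies only to patients already on single-agent nivolumab. It then gives no nivolumab restart rule during combination dosing, and ipilimumab has no authorized partner. This is a gap.

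Neither reading gives the site a usable instruction.

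**Reach.** The conflict between tables applies to all 25 + 15 + 25 = 65 planned patients, including Cohort C and the maintenance phase in A and B. The combination-phase problem applies to 25 + 15 = 40, or 40/65 = 61.5%.

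**Effect on the reported removal proportion, per patient handled differently, at planned numbers.** Cohort A or C: 1/25 = 4.0 percentage points. Cohort B: 1/15 = 6.7. Whole trial: 1/65 = 1.5. These show how coarse the proportions are; they do not predict how many patients would be affected.

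**The case against.** The strongest reply is that this is ordinary specific-over-general drafting: a general table, then detailed organ rules for special cases, which an experienced investigator would follow. That reading is reasonable and probably intended. But it is not stated, and the description of the organ rows as guidance cuts against it.

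A second reply is that only myocarditis says *permanently*, so the other four rows might allow a later restart. The missing restart step and the contrast with grade 2 make a stop the better reading, but it remains an inference.

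Several stronger readings are tempting, and the documents do not support them:

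- That the two grade 3 cells flatly cannot both be followed. This holds only if the single-agent condition limits how nivolumab restarts. Read as describing who the cell covers, it leaves a gap.
- That no organ table agrees with the general table. Renal and skin allow resumption; not repeating the single-agent condition does not put them in conflict with hold-and-resume.
- That the organ conflict is confined to combination dosing. It also applies to nivolumab alone.
- That later nivolumab doses turn on the reading only for colitis. If one site restarts and another stops, exposure differs in all five conflicting tables.
- That nivolumab 480 mg is already barred after a pulmonary, hepatic or neurological stop. Section 5.2.1 sets no organ limit, so the documents leave this open.

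**Conclusion.** The inconsistency is real and should be corrected. For a first grade 3 event, following 5.2.3 as written restarts drug where five of seven graded organ tables stop it: explicitly in myocarditis, and on the most natural reading in the other four. Precedence is not stated, and all three cohorts are affected. In addition, the grade 3 row gives no usable instruction during combination dosing in Cohorts A and B.

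The consequences are for patient safety, consistency between sites and the descriptive proportion removed for adverse events. How many patients would be affected is unknown, because the documents give no grade 3 rate and none is assumed here.

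A reader might infer that the efficacy conclusions are compromised. They are not on this ground: the response cut-offs (2 of 15 and 6 of 25 in Cohort A, 3 of 15 in B, 6 of 25 in C), the power and the type I error do not use the dose-hold rules as inputs.

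The conclusion rests on taking *Discontinue* without a restart step as a stop, and on the reading of *or* given above.

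**What to change.** 1. Add a precedence sentence to 5.2.3:

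> For a first grade 3 event, where an organ-specific row in 5.2.4 says discontinue, that row prevails over this table; the second-grade-3/any-grade-4 row continues to apply.

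The last clause is needed because the skin row covers grades 3 and 4 together and includes a restart, while 5.2.3 removes any grade 4 patient.

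2. Reword the grade 3 row for the combination phase:

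> Hold both drugs. Ipilimumab is not restarted without nivolumab 3 mg/kg. Unless a 5.2.4 row provides for resumption, stop ipilimumab and nivolumab 3 mg/kg; nivolumab 480 mg alone may start at grade 0–1, per 5.2.1.

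This removes the unconditional ipilimumab restart where no organ row applies. Where an organ row does provide for resumption, such as renal or skin, that row governs and the single-agent condition gives way to it.

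3. The sponsor should state whether nivolumab 480 mg may follow an organ-specific discontinuation, other than for myocarditis, under 5.2.1. That is a clinical decision the documents do not settle.

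No wider rewrite is needed: the investigator-discretion sentence and the other organ rules can stay as they are. The cost is a short protocol amendment and somewhat fewer rechallenges.

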Grade 1 Serum creatinine > ULN and > than baseline but \leq 1.5 x baseline	
 Continue nivolumab /or ipilimumab Monitor serum creatinine weekly 	If returns to baseline: 
 Resume creatinine monitoring per protocol If worsens: 
 Treat as Grade 2, 3/4
Grade 2-3 Serum creatinine > 1.5 x baseline to \leq 6 x ULN	
 Delay nivolumab or ipilimumab Monitor serum creatinine every 2-3 days 0.5 to 1.0 mg/kg/day methylprednisolone IV or oral equivalent Consider renal biopsy with nephrology consult 	If returns to Grade 1: Taper steroids over at least 1 month, consider prophylactic antibiotics for opportunistic infections, and resume nivolumab and ipilimumab and routine serum creatine monitoring per protocol If elevations persists > 7days or worsen: 
 Treat as Grade 4
Grade 4 Serum creatinine > 6 x ULN	
 Discontinue nivolumab or ipilimumab Monitor serum creatinine daily 1-2mg/kg/day methylprednisolone IV or IV equivalent Consult nephrology Consult renal biopsy 	If returns to Grade 1: 
 Taper steroids over at least one month and add prophylactic antibiotics for opportunistic infections

5.2.4.8 Myocarditis:

Rule out non-inflammatory causes. If non-inflammatory cause, treat accordingly and continue protocol therapy

Grade of Rash Myocarditis (NCI CTCAE v4)	Management	Follow-up
Grade 2 Symptoms with mild to moderate activity or exertion	
 Delay nivolumab or ipilimumab hospitalization with cardiac monitoring Urgent cardiology consultation for evaluation and management 
 Troponin and BNP ECG ± continuous cardiac monitoring Echocardiogram Cardiac MRI Prompt initiation of 2 mg/kg/day methylprednisolone IV or equivalent 	
 If worsens, intensify treatment according to grade Upon recovery, taper steroids over at least 1 month with close monitoring of troponin and BNP as well as for new symptoms Repeat cardiac MRI for post treatment assessment and cardiology follow-up Retreatment may be considered after recovery and completion of steroid taper

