Grade 3: Severe with symptoms at rest or with minimal activity or exertion; intervention indicated Grade 4: Life threatening consequences; urgent intervention indicated (e.g., continuous IV therapy or mechanical hemodynamic support)	
 Permanently discontinue nivolumab or ipilimumab Hospitalize to intensive cardiac monitoring 
 Cardiac evaluation to include: Troponin and BNP monitoring ECG ± continuous cardiac monitoring Echocardiogram Cardiac MRI Myocardial biopsy if feasible Immediate initiation of 2 mg/kg/day methylprednisolone IV or 1 g IV bolus Consider adding a second immunosuppressive agent 
Additionally, for Grade 4:
 
 Hospitalize/transfer to institution with expertise in intensive cardiac monitoring Consider ATG as second agent given its immediate effect 	
 If no improvement, consider additional immunosuppression Upon recovery, taper steroids over at least 1 month with close monitoring of troponin and BNP as well as for new symptoms Repeat cardiac MRI for post treatment assessments and cardiology follow-up

5.2.4.9 Ocular manifestations:

Monitor patients for signs or symptoms of ocular toxicity, which may include blurred vision and reduced visual acuity. Immune-mediated ocular toxicity may be associated with retinal detachment or permanent vision loss. Administer corticosteroid eye drops to patients who develop uveitis, iritis, or episcleritis. Permanently discontinue ipilimumab for immune-mediated ocular disease that is unresponsive to local immunosuppressive therapy. If uveitis occurs in combination with other immune-mediated adverse reactions, consider a Vogt-Koyanagi-Harada-like syndrome, which has been observed in patients receiving ipilimumab and may require treatment with systemic steroids to reduce the risk of permanent vision loss.

5.2.4.10 Other:

For rare cases of myotoxicity (myositis, myocarditis, and rhabdomyolysis), some with fatal outcome, have been reported with nivolumab or nivolumab in combination with ipilimumab. If a patient develops signs and symptoms of myotoxicity, close monitoring should be implemented, and the patient referred to a specialist for assessment and treatment without delay. Based on severity of myotoxicity, nivolumab or nivolumab in combination with ipilimumab should be withheld or discontinued, and appropriate treatment instituted.

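### The general toxicity table in 5.2.3 says to remove subjects from the trial where 5.5 and 5.6 require follow-up, and its grade 3 row conflicts with the myocarditis table

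*Combined protocol and SAP*

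**What the plan says.** The general table after Section 5.2.3 sets the action for each drug by CTCAE grade.

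- **Second grade 3 or any grade 4 event, both drugs:** "Permanently discontinue therapy and remove subject from trial".
- **Grade 3, nivolumab:** "Withhold drug, resume treatment when adverse reaction improves to grade 0 or 1 when given as a single agent". The ipilimumab cell also allows restart at grade 0 or 1, without the single-agent condition.

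On patients who stop treatment, Section 5.4 lists unacceptable adverse events as a reason to end therapy. Section 5.5 sends all patients who stop to the follow-up in 5.6, and excuses only those who withdraw consent for all procedures or can no longer consent freely. Section 5.6 sets contact every 3 months for 24 months or until death, and follows toxicity stops until the event resolves or stabilizes.

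On organ-specific management, the myocarditis table (5.2.4.8) says "Permanently discontinue nivolumab or ipilimumab" at grade 3 and grade 4. Its only retreatment step is at grade 2: "Retreatment may be considered after recovery and completion of steroid taper". The pneumonitis (5.2.4.1), hepatic (5.2.4.4) and neurological (5.2.4.5) tables say "Discontinue nivolumab or ipilimumab" at grade 3 or 4. The colitis row (5.2.4.2) uses the same verb and adds a reference to the protocol.

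Two sentences link the tables. Section 5.2.3 says the drugs "can only be held or discontinued as per detailed algorithms for immune-therapy toxicity management below". The lead-in to the organ tables reads "Certain adverse events that are possibly immune mediated warrant special monitoring and management, and are outlined below to guide investigators".

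**The concern.** There are two separate problems.

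First, leaving treatment and leaving the trial are different events in this protocol (5.5 against 5.7), and the cell names the second where the follow-up rules assume the first. A site acting on the cell as written would stop collecting AE outcomes and survival status in a group selected by severe toxicity. Section 11.3 reports overall survival by Kaplan-Meier, so those patients would be censored for a reason plausibly related to prognosis. The safety description would also be weakest where it matters most.

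Second, a patient on single-agent nivolumab who recovers from grade 3 myocarditis may be re-exposed under one table and must not be under the other. Section 5.2.4.10 itself notes fatal outcomes in the group of muscle toxicities that includes myocarditis. The trial is multi-center, so sites may resolve the difference in different ways.

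**Working it through.** There is no plan figure to reproduce. The check is a comparison of instructions, plus one line of arithmetic.

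**1. Removal from trial against follow-up**

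| Source | Instruction after a grade 4 or second grade 3 event |
|---|---|
| 5.2.3 general table | Stop therapy and take the subject off the trial (mandatory) |
| 5.4 | An unacceptable adverse event is a reason to end treatment |
| 5.5 | All who stop treatment enter 5.6 follow-up; only consent-related exceptions |
| 5.6 | Quarterly for 24 months; toxicity stops followed to resolution or stabilization |
| 5.7 | Withdrawal from study for safety is allowed at the investigator's discretion; no toxicity grade is listed |
| 8.2 | AEs collected to 100 days after last dose; serious events followed further |

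The cell orders something that 5.5 does not permit. Section 5.7 softens this but does not settle it, because it allows withdrawal for safety and does not require it.

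Follow-up at risk per affected patient on a literal reading: 24 months / 3 months = 8 survival contacts at most (fewer if the patient dies earlier), plus AE-resolution follow-up.

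**2. Restart after a first grade 3 event**

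| Table | Action at grade 3 | Resume step at grade 3 | Resume or retreatment step at grade 2 | Against the general table |
|---|---|---|---|---|
| General (5.2.3), nivolumab | Withhold | Yes, as single agent at grade 0-1 | Yes | n/a |
| Myocarditis | Permanently discontinue | None | Yes | Explicit conflict |
| Pneumonitis | Discontinue | None | Yes | Unclear |
| Hepatic | Discontinue | None | Yes | Unclear |
| Neurological | Discontinue | None | Yes | Unclear |
| Colitis | Discontinue, with a reference to the protocol | None | Yes | Unclear |

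Only the myocarditis row states permanence. Elsewhere the protocol writes *permanently* when it means it: for confirmed SJS/TEN in 5.2.4.6, and for unresponsive ocular disease in 5.2.4.9. The bare verb in the other four rows therefore cannot be taken as an explicit permanent stop. The missing resume step points that way without saying so.

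**3. Is there a precedence rule?** The pointer in 5.2.3 is to algorithms further down, and the general table is itself the first thing below it. The lead-in describes the organ tables as guidance. The instruction in 5.2 to follow the organ system with the greatest toxicity ranks concurrent toxicities, not tables. Section 5.2.4.10 adds that drug is withheld or discontinued by severity for muscle toxicity, including myocarditis, and gives no grades. No sentence says which table governs.

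**The case against.** The best reply is that a sensible reader would reach the intended result on both parts.

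On the first, the protocol uses trial loosely elsewhere. Section 7.2 speaks of taking a patient off the trial at confirmed immune-related progression, then describes the same step as permanent discontinuation of study treatment. Sections 5.5, 5.6, 7.7 and 8.2 all still require follow-up or safety analysis. This largely stands. A reader might infer that the plan builds in loss of follow-up after severe toxicity, and the documents do not support that. What remains is a mandatory cell that a site could act on literally.

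On the second, the general grid is neither detailed nor specific to immune toxicity, and the organ tables are both. The skin table continues drug for grade 2 rash where the general table withholds it, which also suggests that organ tables are meant to prevail. Specific over general is the natural reading, but it has to be inferred.

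Three stronger readings are tempting and should not be taken:

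- **That four or five organ tables conflict with the general table.** Only myocarditis does so explicitly.
- **That investigators may override any stop.** The sentence "Any patient on this protocol will be allowed to continue to receive study treatment at the investigator's discretion, regardless of AE relatedness" sits under a heading on dose delays for related and unrelated events. Nothing there extends it to discontinuation rules.
- **That the single-agent share of the treatment schedule measures the problem.** It is a share of maximum planned time. Exposure also needs a grade 3 event in the relevant organ, recovery to grade 0-1, and a site that follows the general table over the organ table.

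**Conclusion.** The point holds in two limited parts. The removal wording contradicts 5.5 and 5.6 and creates a risk, not a certainty, of losing AE-resolution data and up to 8 survival contacts per affected patient. The grade 3 restart rule conflicts explicitly with one organ table, myocarditis, and no precedence is written. Four further grade 3-4 rows (pneumonitis, hepatic, neurological, colitis) are unclear but not in explicit conflict.

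The number of patients affected cannot be given, because the documents state no expected grade 3 or 4 rate. The data risk assumes that a site reads the cell literally. The safety risk assumes that a site applies the general table to grade 3 myocarditis. Sample size, power and the decision rules are untouched. Severity is low to moderate.

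**What to change.** 1. In both drug columns of the last row of the general table, replace the removal wording with: *permanently discontinue protocol therapy; continue AE and survival follow-up per 5.5, 5.6 and 8.2*.
2. Add to the grade 3 row, for both drugs: *unless the organ-specific table in 5.2.4 calls for permanent discontinuation, which then governs (e.g. grade 3 myocarditis)*.
3. Have the sponsor state in the pneumonitis, hepatic, neurological and colitis grade 3-4 rows whether discontinuation is permanent. This is a clinical decision that the text leaves open, so the review does not prescribe the answer.

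A blanket rule that the stricter instruction applies is not recommended. It would force holds for grade 2 rash, which 5.2.4.6 continues, and would bar restart after grade 4 skin or endocrine events, which 5.2.4.6 and 5.2.4.3 leave open.

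The cost is protocol wording only. The follow-up is already in 5.6, 8.2 and the schedule in 6.1, so no visit, scan or test is added.
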